### **Secondary Analyses**

1) To explore the potential clustering within collaborative care case managers, descriptive statistics of the PHQ-9 at 4 months will be presented grouped by case manager in the intervention arm. The intra-cluster correlation coefficient (ICC) will be calculated to assess between-case-manager variability. The primary analysis will be repeated adjusting for the clustering by case manager by including case managers as a random effect.

2) Any baseline predictors of PHQ-9 scores at 4 months (age, gender, GAD-7, PHQ-15, mental health medication use and previous history of depression based on M.I.N.I. responses) will initially be identified by individual logistic regressions using  $p < 0.10$ , controlling for PHQ-9 at randomisation. Any remaining predictors from a combined regression will be included as covariates in the primary analysis model.

3) In order to investigate the impact of missing data, any baseline predictors of non-response at 4 months follow-up will be included as covariates in the primary analysis model. Non-response will be defined as the absence of a valid PHQ-9 score, and predictors will be identified initially by individual logistic regressions followed by a combined regression using  $p < 0.10$ .

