#### *PHQ-9*

The PHQ-9 is a nine item depression scale. Each item is scored between 0 and 3, thus PHQ-9 scores can range from 0 to 27 with higher scores indicating greater depression. Up to two missing questionnaire items are pro-rated, and no total scores are calculated for responses with more than two missing items. Scores of 5, 10, 15, 20 have been used as cut points for mild, moderate, moderately severe and severe depression.

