#### *Binary Depression Severity*

A logistic mixed effects model will be used to compare PHQ-9 depression caseness (scores  $\geq 10$ ) between treatment arms. The model specification and checking will be similar to the primary analysis, but using depression caseness as the outcome. Any covariates identified for the primary outcome will be included in the model. Odds ratios and 95% confidence intervals will be presented for the effect of the intervention at 4 and 12 months.

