#### *Psychological Anxiety*

The primary analysis will be repeated for the continuous total score of the GAD-7, adjusting for baseline values of the questionnaire and any relevant covariates identified for the primary outcome. Estimates of the effect of the intervention will be derived at 4 and 12 months.

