### **Departures from the Protocol**

Any details specified in the Casper protocol that have been amended in this analysis plan are detailed in Table 2.

Table 2: Departures from Protocol

Protocol Version 2.8 (03/12/ 2013)	Statistical Analysis Plan	Reason for Change
Analyses will be conducted in Stata version 10.	Analyses will be conducted in Stata version 13 or later.	Latest analytical software should be used.
The statistician conducting the analyses will remain blind to treatment group until all data summaries and results are finalised.	The statistician will be kept blind to group allocation until the primary analysis has been completed and checked by the second statistician.	Some of the trial data explicitly reveal treatment allocation, and it would not be feasible to ensure blindness throughout.
A logistic regression model will be used to compare collaborative care with usual care on the primary outcome.	A covariance pattern linear mixed effects model will be used to compare collaborative care with usual care on PHQ-9 scores at 4 months.	Including the word 'logistic' was an error in the protocol, as the primary PHQ-9 outcome is continuous. In order to maximise the use of available data, mixed models will be used instead of individual regressions at each time point.
Appropriate sensitivity analyses will be used to examine the effects of missing data on outcomes.	In order to investigate the impact of missing data, any predictors of non-response will be included as covariates in the primary analysis model only.	As the analysis of secondary outcomes is more exploratory in nature, the sensitivity analysis was restricted to the primary outcome only.
Binary PHQ-9 not mentioned.	Binary PHQ-9 (cut-off: $\geq 10$ score points) at 4 and 12 months will be included as a secondary outcome.	The published protocol paper lists binary description of the PHQ-9 as a secondary outcome and has been omitted in error from the full protocol.
To explore the potential clustering within collaborative care case managers the primary analysis will be repeated adjusting for the clustering using the Huber-White standard estimator (robust standard errors).	The primary analysis will be repeated adjusting for the clustering by case manager by including case managers as a random effect.	As the primary analysis is now a mixed model, a random effect for case managers is appropriate.

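### Predictors of the continuous 4-month PHQ-9 score are screened by logistic regression with no cut-off, and the screen appears to set covariates for the binary PHQ-9, SF-12, GAD-7 and medication models

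*SAP*

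**What the plan says.** Under Secondary Analyses of the primary outcome, item 2 targets "Any baseline predictors of PHQ-9 scores at 4 months". The six candidates are "age, gender, GAD-7, PHQ-15, mental health medication use and previous history of depression based on M.I.N.I. responses". They "will initially be identified by individual logistic regressions using" p < 0.10, controlling for PHQ-9 at randomisation. Those that remain after a combined regression are added to the primary model, which is a linear mixed model. The PHQ-9 section states that "PHQ-9 scores can range from 0 to 27", and item 2 names no cut-off.

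Table 2 (Departures from the Protocol) explains why the primary comparison is no longer logistic: "Including the word 'logistic' was an error in the protocol, as the primary PHQ-9 outcome is continuous".

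The analyses of secondary outcomes then refer back to identified covariates:

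- Binary Depression Severity: "Any covariates identified for the primary outcome will be included in the model".
- Psychological Anxiety: adjustment for baseline GAD-7 and "any relevant covariates identified for the primary outcome".
- Quality of Life (SF-12 PCS and MCS) and Mental Health Medication: the same phrase, also limited to 'relevant' covariates.

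No other model is stated for these outcomes. PHQ-9 at 12 months is taken directly from the primary model.

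**The concern.** Logistic regression needs a binary (or at least categorical) outcome, and item 2 names a score. The analyst must therefore make a decision that the plan does not record: dichotomise at some cut-off (perhaps the ≥10 used for caseness elsewhere), fit an ordinal model, or read the word as a slip for linear. Each choice could select a different set of covariates. The reason given in Table 2 for removing 'logistic' from the comparison model applies equally here.

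The result matters beyond one sensitivity analysis. It appears to determine the adjustment set of the only stated model for binary PHQ-9, SF-12 PCS and MCS, GAD-7 and medication. For all but binary PHQ-9, someone must also decide which identified covariates are relevant, with no criterion. The Blinding section says that work after the primary analysis is unblinded. Because Analysis Population requires complete covariates and Principles rules out imputation, the choice can also change which patients are analysed.

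**Working it through.** **The text, side by side**

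| Place in SAP | Outcome | Method | Match? |
|---|---|---|---|
| Primary Analysis | PHQ-9 score, 4 and 12 months | linear mixed model, two fixed covariates | yes |
| Secondary Analyses, item 2 | PHQ-9 score, 4 months | logistic screen, no cut-off | no |
| Secondary Analyses, item 3 | non-response (yes/no) | logistic screen | yes |
| Table 2 | PHQ-9 score | 'logistic' called an error | – |

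**The plan's own figure.** With 0.3 SD, 80% power and two-sided 5%, a t-based calculation gives 175.4, so 176 per arm (352). The design effect is 1 + 19 × 0.02 = 1.38, and 352 × 1.38 = 485.8, so 486. Per arm, 243/0.74 = 328.4, so 329 (658 in total). All three stated sizes reproduce. I use 486 as the number analysed.

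**Information kept if the score is dichotomised.** The case rate is an assumption; the SAP gives none. For a normal outcome split so that a proportion p are cases, the relative efficiency is φ(z_p)² / [p(1 − p)]:

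- p = 0.20: 0.2800² / 0.16 = 0.490
- p = 0.30: 0.3477² / 0.21 = 0.576
- p = 0.50: 0.3989² / 0.25 = 0.637

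**Chance that a real predictor passes p < 0.10.** Assume partial correlation r = 0.12 (not in the SAP) and 486 − 3 = 483 degrees of freedom. The probability is Φ(r√483 × √efficiency − 1.645):

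- Linear: 0.12 × 21.98 = 2.637; Φ(0.992) = 0.84
- Dichotomised, 20% cases: 2.637 × 0.70 = 1.846; Φ(0.201) = 0.58

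**Simulation check** (N = 486, correlation of 0.5 with baseline PHQ-9, 600 runs per setting, all assumed):

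| Standardised effect | Caseness | Linear screen | Logistic screen |
|---|---|---|---|
| 0.10 | 15% | 82% | 45% |
| 0.10 | 25% | 79% | 56% |
| 0.10 | 40% | 83% | 60% |
| 0.15 | 15% | 98% | 75% |
| 0.15 | 25% | 98% | 79% |
| 0.15 | 40% | 99% | 90% |

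An effect of 0.10 here is a partial correlation of about 0.10/√0.75 = 0.115, so the simulation and the formula agree.

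**Effect on the treatment test.** A linear screen of six candidates that ignored arm, three of them with a true effect of 0.1, was followed by the treatment test on the same outcome. In 3,000 runs under the null, type I error was 0.056. The Monte Carlo standard error is √(0.05 × 0.95/3000) ≈ 0.004, so the excess over 0.05 is about 1.5 standard errors.

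**The case against.** The strongest reply is that 'logistic' in item 2 is a one-word carry-over. Item 3, just below, uses the same phrase correctly for binary non-response. Item 2 speaks of scores, feeds a linear model and gives no cut-off, so a sensible analyst would fit linear regressions. Table 2 corrects the comparison model and says nothing about the screen. PHQ-9 at randomisation is loose wording that footnote 2 of Table 1 largely settles, since it names the diagnostic-interview score as the covariate. The phrase about identified covariates could also mean the two fixed covariates of the primary model, or the item 3 predictors. The SAP itself calls the secondary-outcome analyses more exploratory.

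Much of this stands and limits the weight of the point. It does not remove it: the intended method has to be guessed, and the possible second and third meanings of 'identified' are a further ambiguity. Item 2 uses the same verb, so it remains the natural referent.

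A reader might infer more than the document supports:

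- *That every modelled secondary outcome is affected.* PHQ-9 at 12 months comes from the primary model with its fixed covariates.
- *That the selection is post hoc.* The candidates, the entry threshold and the two-step rule are laid down in advance. The undefined element is 'relevant'.
- *That treatment effects are biased or error rates inflated.* The simulation does not show it.
- *That a 47% chance of a spurious covariate follows from the logistic error.* That figure, 1 − 0.9⁶ = 0.469, assumes six independent null candidates and is the same for a linear screen.

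**Conclusion.** Item 2 is wrong as written and should be corrected before analysis. The harm is an ill-defined and, if the score is dichotomised, less efficient adjustment set. On the natural reading it reaches the only stated models for binary PHQ-9, SF-12 PCS and MCS, GAD-7 and medication, with unblinded discretion over what is relevant in all but the first.

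The loss is in covariate selection: selection in about 58% instead of 84% of trials, resting on an assumed 20% case rate, r = 0.12 and 486 patients. Over assumed case rates of 15% to 40%, simulation gives 45–60% against 79–83% for a standardised effect of 0.10. These figures do not measure error in a treatment effect. The primary analysis and the sample size are untouched. This is a should-fix point.

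**What to change.** 1. In item 2, replace 'logistic' with 'linear' and state the threshold for staying in the combined regression, which is given for item 3 but not here. Alternatively, drop the screen and fit the primary linear mixed model with all six named covariates.
2. Replace PHQ-9 at randomisation with PHQ-9 at the diagnostic interview, in line with footnote 2 of Table 1.
3. For binary PHQ-9, SF-12 PCS, SF-12 MCS, GAD-7 and medication, replace the reference to identified or relevant covariates with a fixed list: the baseline value of that outcome where collected, PHQ-9 at the diagnostic interview, and baseline SF-12 PCS (listed once when PCS is the outcome).

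The cost is SAP wording, with no change to sample size. Fitting all six covariates uses a few degrees of freedom among about 486 patients. It also drops patients with a missing covariate, because no imputation is planned, so the number analysed should be reported for each model.

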#### Sample Size

To detect a minimum standard effect size of 0.3 with 80% power and a two-sided 5% significance level would require 352 patients (176 in each group). Although this is an individually-randomised trial, there may be potential clustering at the level of each collaborative care case manager and hence the sample size was inflated to account for this. Based upon an ICC = 0.02 and a caseload size of 20, the design effect would be 1.38 ( $1 + (20 - 1) \times 0.02$ ) and 486 patients (243 in each group) would be required.

The original trial sample size allowed for 10% loss to follow-up, resulting in a total of 540 patients (270 in each group). Following the inspection of interim recruitment figures and disproportionate dropout from the collaborative care arm, this assumption was revised (Substantial Amendment 17). Allowing for a loss to follow-up of 26%, the final sample size needed is 658 patients (329 in each group).

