#### Randomisation

Participants with sub-threshold depression who met the inclusion criteria, provided written consent and were not actively receiving psychological therapy were eligible for randomisation into the trial. Once invitation, baseline and diagnostic interview data were collected and entered into the study database, randomisation was carried out by the York Trials Unit Randomisation Service. Participants were randomised on a 1:1 basis using simple randomisation to either the intervention group (collaborative care) or control group (usual care).

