## **6. Analysis**

### **Principles**

All analyses will be conducted on intention to treat basis (ITT), including all randomised participants in the groups to which they were allocated. Any post randomisation exclusions will be referred to the independent statistician on the DMEC for approval. Analyses will be conducted in Stata version 13 or later, using 2-sided significance tests at the 5% significance level. Results will be presented with 95% confidence intervals where appropriate. The statistician conducting the analyses will remain blind to treatment group until the primary analysis is finalised and checked by the second statistician.

Any missing data will be reported for all predictor and outcome variables by trial arm and response rates compared. No imputations will be undertaken, and the impact of missing data will be explored as part of secondary analyses of the primary outcome.

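### Dropout is known to be higher in collaborative care, yet no planned analysis tests how far the 4-month PHQ-9 result depends on dropout related to unobserved scores

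*SAP*

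**What the plan says.** Under Sample Size, the SAP explains why the loss allowance was changed: "Following the inspection of interim recruitment figures and disproportionate dropout from the collaborative care arm, this assumption was revised". The allowance rose from 10% to 26% and the target from 540 to 658 patients. Dropout rates by arm are not given.

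Under Analysis of the Primary Outcome, the primary analysis is a covariance pattern mixed model for PHQ-9 at 4 and 12 months. It is adjusted for PHQ-9 at the diagnostic interview and the baseline SF-12 physical score. Analysis Population limits it to patients with at least one follow-up PHQ-9 and complete baseline covariates.

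On missing data, Principles says "No imputations will be undertaken" and leaves the question to the secondary analyses of the primary outcome. The third of these is the relevant one: "any baseline predictors of non-response at 4 months follow-up will be included as covariates in the primary analysis model". The predictors are found by logistic regression at p < 0.10, and no modelling of non-response by arm is mentioned. The Departures from the Protocol table presents this as the replacement for the protocol's general commitment to sensitivity analyses. The reason given there explains only why it covers the primary outcome alone.

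The rest is descriptive: missingness and response rates by arm, dropout types and reasons by arm, and baseline tables for all randomised and for all analysed participants.

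**The concern.** A likelihood-based mixed model is valid if, given its covariates and the observed PHQ-9 scores, the missing scores follow the same distribution as the observed ones. Unequal dropout does not break that assumption, but it gives a specific reason to doubt it: something about one arm is leading people to leave. The trial is unblinded and its outcome is self-reported, so whether someone returns a questionnaire may well depend on how they feel at the time, beyond what baseline variables record.

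A sensitivity analysis should vary the assumption in doubt. The planned one keeps MAR and enlarges the set of variables conditioned on. A variable that predicts response but not PHQ-9 leaves the estimate essentially unchanged. If non-response depends on the unseen 4-month score itself, no baseline covariate fully restores what is lost. Agreement between this analysis and the primary result could then be read as robustness that was never tested.

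**Working it through.** **1. The plan's own figures**

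Inputs from Sample Size: effect 0.3 SD, 80% power, two-sided 5%, ICC 0.02, caseload 20, loss of 10% and then 26%. Randomisation gives 1:1 allocation.

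- A two-sample t-test needs 175.4 per arm, so 176 per arm and 352 in total.
- Design effect: 1 + 19 × 0.02 = 1.38; 352 × 1.38 = 485.8, so 486 (243 per arm).
- 10% loss: 243 / 0.90 = 270 per arm, 540 in total.
- 26% loss: 243 / 0.74 = 328.4, so 329 per arm, 658 in total.

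All the stated figures reproduce.

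**2. Bias from a departure from MAR**

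Let p be the fraction missing in an arm and δ the amount by which its missing patients score worse than the model predicts. Then

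bias in favour of collaborative care (CC) over usual care (UC) = p_CC × δ_CC − p_UC × δ_UC.

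A negative δ (leavers doing better than predicted) reverses the sign. The SAP gives no arm split, SD or δ. The values below are assumptions: splits that average 26%, SD 4.5 points, δ from 1 to 3 points.

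| Missing CC/UC | δ (points) | CC only | Same δ in both arms |
|---|---|---|---|
| 30%/22% | 1 | 0.30 × 1 / 4.5 = 0.07 SD | 0.08 × 1 / 4.5 = 0.02 SD |
| 36%/16% | 2 | 0.36 × 2 / 4.5 = 0.16 SD | 0.20 × 2 / 4.5 = 0.09 SD |
| 40%/12% | 3 | 0.40 × 3 / 4.5 = 0.27 SD | 0.28 × 3 / 4.5 = 0.19 SD |

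**3. Tipping point for a result equal to the target**

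Take an MAR estimate of 0.30 SD with 329 randomised per arm and SE = √(1.38/n_CC + 1.38/n_UC), where n is the number observed. For 36%/16%: n = 210.6 and 276.4, SE = 0.1075. Significance is lost in the CC-only case at δ = (0.30 − 1.96 × 0.1075) / 0.36 = 0.25 SD.

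| Missing CC/UC | Significance lost, CC only | Significance lost, same δ in both | Estimate zero, CC only |
|---|---|---|---|
| 26%/26% | 0.35 SD | never (no bias) | 1.15 SD |
| 31%/21% | 0.29 SD | 0.91 SD | 0.97 SD |
| 36%/16% | 0.25 SD | 0.45 SD | 0.83 SD |
| 40%/12% | 0.22 SD | 0.31 SD | 0.75 SD |

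At the assumed SD, 0.22 to 0.35 SD is about 1.0 to 1.6 PHQ-9 points.

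**4. What adding a predictor of non-response does**

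This is an illustrative simulation with 400,000 patients, one follow-up time, 36%/16% missing and assumed coefficients. Entries are the apparent benefit of CC.

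| Non-response in CC depends on | True effect | Without predictor | With predictor |
|---|---|---|---|
| a baseline variable only | 0 | 0.05 SD | 0.00 SD |
| that variable and the unseen PHQ-9 | 0 | 0.23 SD | 0.17 SD |
| that variable and the unseen PHQ-9 | 0.30 SD | 0.52 SD | 0.46 SD |

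The planned analysis corrects the first mechanism and leaves most of the bias from the second.

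**The case against.** Much can be said for the plan, and several stronger readings do not follow from it.

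- **A reader might infer that the planned check is worthless.** It is not. Adding predictors of non-response usually makes MAR more plausible, and where non-response is explained by recorded baseline variables it removes the bias. The 12-month score also helps for patients missing only at 4 months. The limit concerns dropout related to unobserved PHQ-9.
- **A reader might infer that ruling out imputation makes any MNAR analysis impossible.** It does not. Pattern-mixture models, selection models and an analytic shift like the one in the working need no imputed values.
- **A reader might assume that those who leave collaborative care do worse, so that the bias favours the intervention.** The SAP does not give the direction. People with sub-threshold symptoms may also leave because they feel well.
- **A reader might quote 0.16 SD alone.** That sets the usual care departure to zero. The same shift in both arms gives 0.09 SD.
- **The dropout imbalance may overstate the imbalance in missing PHQ-9.** The SAP counts leaving treatment as one kind of dropout and continues follow-up after withdrawal from the intervention alone. However, it raised the loss to follow-up allowance in response, so it did not regard the imbalance as confined to treatment sessions.
- **The descriptive tables by arm** will expose the imbalance and help to judge which shifts are plausible. They do not test how far the estimate depends on it.

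These points narrow the concern. None of them supplies the missing analysis.

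**Conclusion.** The concern holds in a limited form. The primary model is reasonable and the covariate-based check is useful, but the SAP pre-specifies nothing that departs from MAR, although it records unequal dropout itself. Dependence of the 4-month result on unobserved PHQ-9 therefore stays untested.

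The possible size is not negligible against the 0.3 SD target: 0.07 to 0.27 SD if only collaborative care departs from MAR, and 0.02 to 0.19 SD if both arms depart equally. These figures rest on assumed arm splits, an assumed SD of 4.5 and assumed shifts of 1 to 3 points. They show what could go undetected and are not an estimate of the bias in this trial. The documents do not support a claim that the result will be biased, or biased in a particular direction.

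**What to change.** Keep the mixed model as the primary analysis and keep the third secondary analysis. Add a pre-specified MNAR sensitivity analysis for PHQ-9 at 4 months that includes randomised patients with no follow-up score. One suitable form is:

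- multiple imputation by arm, using the baseline covariates, the predictors of non-response already planned, and the 4- and 12-month PHQ-9;
- shifts added to the imputed values, for example 0, 1, 2 and 3 points in each direction, varied separately by arm and in both arms together;
- a report of the shift at which the 4-month conclusion changes, read beside the dropout reasons by arm.

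Either exempt this analysis from the statement "No imputations will be undertaken", or use a pattern-mixture shift that needs no imputation. Fix the range of shifts before allocation is revealed. The analysis itself can follow the primary analysis, when the SAP already allows unblinded work.

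The cost is a paragraph in the SAP and modest extra Stata programming. No new data are needed, and the primary analysis and sample size do not change.
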